## 15.0 RESEARCH PARTICIPANT REGISTRATION AND RANDOMIZATION PROCEDURES

### 15.1 Research Participant Registration

Confirm eligibility as defined in the section entitled Criteria for Patient/Subject Eligibility.

Obtain informed consent, by following procedures defined in section entitled Informed Consent Procedures.

During the registration process registering individuals will be required to complete a protocol specific Eligibility Checklist.

All participants must be registered through the Protocol Participant Registration (PPR) Office at Memorial Sloan-Kettering Cancer Center. PPR is available Monday through Friday from 8:30am – 5:30pm at [contact]. Registrations must be submitted via the PPR Electronic Registration System (<http://ppr/>). The completed signature page of the written consent/RA or verbal script/RA, a completed Eligibility Checklist and other relevant documents must be uploaded via the PPR Electronic Registration System.

## 16.0 DATA MANAGEMENT ISSUES

A Research Study Assistant (RSA) will be assigned to the study. The responsibilities of the RSA include project compliance, data collection, abstraction and entry, data reporting, regulatory monitoring, problem resolution and prioritization, and coordinate the activities of the protocol study team.

The data collected for this study will be entered into a secure database. Source documentation will be available to support the computerized patient record.

Amended: 02/24/15

## Memorial Sloan-Kettering Cancer Center IRB Protocol

IRB#: 09-159A(10)

### 16.1 Quality Assurance

Weekly registration reports will be generated to monitor patient accruals and completeness of registration data. Routine data quality reports will be generated to assess missing data and inconsistencies. Accrual rates and extent and accuracy of evaluations and follow-up will be monitored periodically throughout the study period and potential problems will be brought to the attention of the study team for discussion and action.

Random-sample data quality and protocol compliance audits will be conducted by the study team, at a minimum of two times per year, more frequently if indicated.

### 16.2 Data and Safety Monitoring

The Data and Safety Monitoring (DSM) Plans at Memorial Sloan-Kettering Cancer Center were approved by the National Cancer Institute in September 2001. The plans address the new policies set forth by the NCI in the document entitled "Policy of the National Cancer Institute for Data and Safety Monitoring of Clinical Trials" which can be found at: <http://cancertrials.nci.nih.gov/researchers/dsm/index.html>. The DSM Plans at MSKCC were established and are monitored by the Office of Clinical Research. The MSKCC Data and Safety Monitoring Plans can be found on the MSKCC Intranet at: <http://inside2/clinresearch/Documents/MSKCC%20Data%20and%20Safety%20Monitoring%20Plans.pdf>

There are several different mechanisms by which clinical trials are monitored for data, safety and quality. There are institutional processes in place for quality assurance (e.g., protocol monitoring, compliance and data verification audits, therapeutic response, and staff education on clinical research QA) and departmental procedures for quality control, plus there are two institutional committees that are responsible for monitoring the activities of our clinical trials programs. The committees: *Data and Safety Monitoring Committee (DSMC)* for Phase I and II clinical trials, and the *Data and Safety Monitoring Board (DSMB)* for Phase III clinical trials, report to the Center's Research Council and Institutional Review Board.

During the protocol development and review process, each protocol will be assessed for its level of risk and degree of monitoring required. Every type of protocol (e.g., NIH sponsored, in-house sponsored, industrial sponsored, NCI cooperative group, etc.) will be addressed and the monitoring procedures will be established at the time of protocol activation.

Institutional monitoring plan for phase I and phase II trials: Memorial Sloan-Kettering Cancer Center (MSKCC) has established standard procedures for data safety monitoring of clinical research (see appendix). For Phase II trials, these procedures include consideration of accrual rates, toxicity, adherence to dose-escalation schedules, adverse event notification and data recording.

Amended: 02/24/15

## Memorial Sloan-Kettering Cancer Center IRB Protocol

IRB#: 09-159A(10)

Therapeutic responses are logged on a central database and approximately 50% are reviewed by an independent committee. An annual report of the trial's progress is sent to the IRB. All of the procedures for Phase II studies outlined in MSKCC's policy are applicable to the current trial and will be followed by the investigators. The analysis of safety will include all patients who receive at least one dose of study medication. Adverse events, including all toxic effects of treatment, will be tabulated individually, and summarized by body system, according to dosage of study medication (single dose as well as cumulative doses of 3F8 and GM-CSF), and according to severity or toxicity grade. Laboratory data will be tabulated and summarized by descriptive statistics, as well as on the basis of MSKCC specified normal ranges.

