#### Secondary Objectives

- Apply real-time quantitative RT-PCR to test the hypothesis that the minimal residual disease content of bone marrow after the first treatments with 3F8/GM-CSF has significant prognostic impact on relapse-free survival.
- Monitor safety of the high-dose antibody treatment, to assure no side-effects or noxious sequelae develop or emerge that were not seen in the prior phase I study.

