### 4.0 OVERVIEW OF STUDY DESIGN/INTERVENTION

#### 4.1 Design

This phase II, open-label, single arm trial assesses the anti-NB activity of high-dose 3F8 (80 mg/m^2/day), which is used in cycles 1-2, with return to standard 3F8 dosage (20 mg/m^2/day) in subsequent cycles. Clinical results will be compared to those in the predecessor trials which used only the standard 3F8 dosage.

Starting with A(8), patients no longer receive high dose 3F8 but receive only standard dose 3F8 (20mg/m^2/day) for all cycles.

The patients are in 1st complete/very good partial remission (CR/VGPR) after conventional therapy, with no evidence of NB by standard studies, but are at high risk for relapse.

Real-time quantitative RT-PCR will be used to assess MRD in BM. 13-*cis*-retinoic acid is started after cycle 2.

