## Memorial Sloan-Kettering Cancer Center IRB Protocol

IRB#: 09-159A(10)

a full 5-day cycle. GM-CSF will be continued through the 3F8 make-up day at the 500 mcg/m^2 dose.

\*High-dose 3F8 will be administered only for patients enrolled on protocol from A(0) to A(7). Starting with A(8), patients receive standard dose (20mg/m^2/day) during cycles 1 and 2.

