### 9.0 TREATMENT/INTERVENTION PLAN

**9.1 Schedule:** For patients consented on A(0) to A(7), 3F8 is dosed at 80 mg/m^2/day (cycles 1-2) or 20 mg/m^2/day (cycles 3 and beyond) and infused iv over 30-90 minutes. Starting with A(8), patients receive 3F8 at 20 mg/m^2/day for all cycles. To modulate pain from 3F8, patients are premedicated with analgesics (e.g., hydromorphone) and antihistamines (e.g., diphenhydramine or hydroxyzine). 3F8 is started ~1 hr after GM-CSF. GM-CSF is dosed at 250 mcg/m^2/day from day -5 to day +1 (i.e. Wednesday to Tuesday is customary), and is 500 mcg/m^2/day on days +2 to +4 (i.e. Wednesday to Friday), as in the predecessor protocols. Patients come off study if progressive disease occurs or if there is life-threatening grade 4 toxicity from 3F8.

The break from end of a cycle to start of next cycle is approximately 2-to-4 weeks through 4 cycles; subsequent breaks are ~6-8 weeks. 13-cis-retinoic acid is started after cycle 2. Road map/schema is in section 4.2.

Patients who develop HAMA which precludes timely treatments with 3F8/GM-CSF are eligible to receive low-dose maintenance regimens such as irinotecan alone temozolomide alone, irinotecan-temozolomide, or cyclophosphamide-topotecan. They can also receive anti-HAMA agents such as rituximab and cyclophosphamide. They resume treatment with 3F8/GM-CSF if HAMA becomes negative.

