### 13.0 CRITERIA FOR REMOVAL FROM STUDY

**13.1** PD any time after cycle 1. However, if a patient develops recurrent disease that can be completely eliminated surgically or eliminated by other means, that patient may remain on study at the discretion of the Principal Investigator as long as the patient does not receive systemic therapy and the recurrence is promptly eliminated.

**13.2** Life-threatening grade 4 toxicity clearly attributable to 3F8.

**13.3** The investigators will make every reasonable effort to keep each patient in the study until all planned treatments and assessments have been performed. The investigators may discontinue study drug treatment for the following reasons:

- **Adverse events**, including unacceptable toxicity or exacerbation of underlying disease, associated with study drug administration and necessitating discontinuation of treatment. Patients who are removed from the study due to adverse events will be treated and followed according to established, acceptable medical practice. All pertinent information concerning the outcome of such treatment will be entered in the Case Report Form or on the Serious Event Report, as applicable.
- **Withdrawal of consent.** The patient's desire to withdraw from the study may occur at any time. The investigator should carefully consider whether the patient's withdrawal of consent is due to an adverse event, and if so, record the adverse event as the reason for withdrawal.
- **Withdrawal by the physician** for clinical reasons not related to study drug treatment, for example, clinical need to administer a concomitant medication that is excluded by the protocol, in the absence of an adverse event.
- **Violation of the study protocol**, including failure to return for required treatments or assessments. Patients who fail to return for treatments will be withdrawn from the study if more than 4 scheduled doses are missed

**13.4** Patients will not be removed from study in order to receive radiotherapy.

**13.5** Patients removed from the study will not be replaced. Every effort will be made to follow these patients, with extent-of-disease evaluations performed at least every 3 months through ≥2 years from study enrollment.

Amended: 02/24/15

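### Section 16.2 tabulates adverse events by 3F8 dose without a split by cycle or amendment cohort, so a difference between dose columns cannot be read as a dose effect

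*Combined protocol and SAP*

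**What the plan says.** The secondary objectives in Section 2.0 include "Monitor safety of the high-dose antibody treatment", with the aim of making sure that nothing appears that the phase I study had not shown. Section 16.2 sets the safety population: "The analysis of safety will include all patients who receive at least one dose of study medication". It then has adverse events tabulated individually and summarized by body system, and "according to dosage of study medication (single dose as well as cumulative doses of 3F8 and GM-CSF), and according to severity or toxicity grade". Cycle number and amendment cohort are not among the classifiers.

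The dose sequence is fixed. Section 4.1 describes the high dose as one "which is used in cycles 1-2, with return to standard 3F8 dosage". Section 9.1 then states: "Starting with A(8), patients receive 3F8 at 20 mg/m 2 /day for all cycles". Section 14.0 keeps the A(8)-onward patients evaluable for toxicity only.

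Three other provisions depend on time on study:

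- Section 9.3 starts 13-cis-retinoic acid after cycle 2, or sooner if early HAMA develops.
- Section 13 removes patients for progression after cycle 1, and for "Life-threatening grade 4 toxicity clearly attributable to 3F8".
- Section 11.1 records every grade in cycle 1 but only grade 3 or higher afterwards.

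**The concern.** Dose is the classifier that the plan chose, so a reader of the table will naturally compare the 80 mg/m2 column with the 20 mg/m2 column and call the difference a dose effect. In the high-dose cohort, though, the 80 column consists entirely of a patient's first two exposures. The 20 column for the same patients consists entirely of later cycles, in those still on treatment. An excess at 80 could come from the dose, from first exposure, or from the loss of patients who tolerated treatment poorly. Equally, a real dose effect could be blurred. The trial does hold the observations needed for a fairer description, namely cycles 1-2 at 20 mg/m2 in the A(8)-onward cohort, but Section 16.2 merges them with everyone's later cycles.

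**Working it through.** The plan states no figure on this point, so there is nothing to reproduce. The check asks what a dose-classified table can identify, and then gives an illustration of size.

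**1. Dose by cycle and cohort** (Sections 4.1, 4.2, 9.1, 9.2), in mg/m2/day:

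| Cohort | Cycles 1-2 | Cycle 3 onward |
|---|---|---|
| A(0)-A(7) | 80 | 20 |
| A(8) onward | 20 | 20 |

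A table by daily dose alone puts the top-left cell in one column and pools the other three in the second.

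**2. Can dose be separated from cycle order?** Take a model with an intercept, an indicator for 80 mg/m2 and an indicator for cycles 1-2.

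- A(0)-A(7) alone: the two indicators are identical in every cycle (correlation 1.0), so the three columns have rank 2. The aliasing is complete.
- With A(8)-onward patients added: rank 3 of 3, or 4 of 4 with a cohort term. Dose and cycle order can be separated, but only if cycle and cohort are kept in the table.

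**3. Does cumulative dose separate them?** With five days per cycle, 5 x 80 = 400 and 5 x 20 = 100 mg/m2 per cycle.

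- A(0)-A(7), after each cycle: 400, 800, 900, 1000, ...
- A(8) onward: 100, 200, 300, ..., reaching 800 after cycle 8 and 900 after cycle 9.

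A cumulative-dose bin at 800 therefore mixes cycle 2 at 80 with cycle 8 at 20. At 900 it mixes cycle 3 of one cohort with cycle 9 of the other.

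**4. Illustration with no dose effect.** Let e and l be the event rates per cycle in cycles 1-2 and later, k the number of later cycles per patient, and nH and nS the numbers of high-dose and A(8)-onward patients. Attrition is ignored.

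Rate in the 20 column = [nH x k x l + nS x (2e + k x l)] / [nH x k + nS x (k + 2)]. The rate in the 80 column is e.

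*Assumed 2:1* (e = 0.30, l = 0.15, k = 6, nH = 40):

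- nS = 0: 36/240 = 0.150, ratio 2.00
- nS = 10: 51/320 = 0.159, ratio 1.88
- nS = 20: 66/400 = 0.165, ratio 1.82
- nS = 40: 96/560 = 0.171, ratio 1.75

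*Assumed 3:1* (e = 0.30, l = 0.10). The Section 4.2 road map, with a one-week cycle and mid-range breaks of 3 and 7 weeks, gives 15 cycle starts before week 104, hence k = 13. Breaks of 2 and 6 weeks give 17 starts, and breaks of 4 and 8 weeks give 13. With the patient numbers expressed as shares:

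- A(8)-onward share 20%: (0.8 x 1.3 + 0.2 x 1.9) / (0.8 x 13 + 0.2 x 15) = 1.42/13.4 = 0.106, ratio 2.8
- Share 50%: (0.5 x 1.3 + 0.5 x 1.9) / (0.5 x 13 + 0.5 x 15) = 1.60/14 = 0.114, ratio 2.6

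With k = 6 instead, the 3:1 assumption gives 0.72/6.4 = 0.1125 (ratio 2.7) at a 20% share and 0.90/7 = 0.129 (ratio 2.3) at 50%.

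In every case the comparison restricted to cycles 1-2 across cohorts gives 0.30/0.30 = 1.0.

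**The case against.** The best defence is that the protocol never sets out to estimate 80 against 20 mg/m2. Its safety objective is to notice effects not seen in phase I. Individual tabulation by body system and grade serves that aim whatever the cycle order. This stands, and it limits the point: the table is descriptive, and no inference about dose is planned from it.

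A reader might go further and infer that the dose table is the only safety summary, so that the high-dose safety objective fails. The documents do not support that. Section 16.2 also plans individual and laboratory tabulations, Section 17.2 adds serious event reporting, and an institutional monitoring policy applies whose text is not reproduced.

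A reader might also infer that early removal for severe toxicity places such patients in low cumulative-dose bins and so reverses the dose trend. That would follow only if events were classed by each patient's final total, and Section 16.2 does not say final. If cumulative dose were taken at the time of the event and cross-classified with daily dose, cycles 1-2 at 20 mg/m2 would show up under full dosing at 100-200 mg/m2, a cell that no fully dosed A(0)-A(7) patient can fill. The wording does not promise that cross-classification, so the gap remains, but as one of specification.

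Finally, the cross-cohort comparison is not clean. The cohorts are sequential and non-randomised. Sections 10.10 and Table 1 require at least two days of blood pressure monitoring after 3F8 at 80 mg/m2 and drop it from A(8). Section 11.2.2 defines unacceptable hypertension by medication lasting more than 24 hours. High-dose patients therefore had a longer mandated observation window for exactly that event. This objection stands in full and shapes the fix.

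**Conclusion.** The point holds as a gap in the specification of a descriptive table. Within A(0)-A(7), dose and cycle are completely aliased, and Section 16.2 as written gives no split that would undo this. A difference between its dose columns therefore cannot be read as a dose effect. This rests on the dosing schedule alone and needs no assumption.

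The size does rest on assumptions. The apparent ratio of about 1.75 to 2.8 under no dose effect follows from assumed early-to-late event rates of 2:1 to 3:1, assumed numbers of cycles, and an A(8)-onward share that the documents do not give. It shows how large a misreading could be and is not a forecast. It would be wrong to conclude that the trial's data cannot address the question at all, because the A(8)-onward patients make a matched description possible. The table also remains able to list events seen at 80 mg/m2. The primary endpoint is not affected.

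**What to change.** In Section 16.2:

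- Tabulate adverse events by cycle block (1-2 versus 3 onward) and amendment cohort (A(0)-A(7) versus A(8) onward), with the number of patients at risk in each cycle.
- Base any high- versus standard-dose description on the per-patient incidence of grade 3 or higher toxicity in cycles 1-2 across the two cohorts, with exact 95% intervals. Restricting it to grade 3 or higher avoids the change in recording after cycle 1.
- State that cumulative dose means the dose received before the cycle in which the event occurred.
- Leave hypertension out of the cross-cohort comparison, or flag it for unequal monitoring.
- State that the cohorts are sequential and non-randomised, and report the A(8)-onward number, since it determines the precision.

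The cost is a re-cut of data that the protocol already collects. No new assessments are needed. The remaining weakness is the non-concurrent comparison, which has to be stated alongside the results.

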### 17.0 PROTECTION OF HUMAN SUBJECTS

The investigator agrees to conduct this study in accordance with the International Conference on Harmonization (ICH) principles of Good Clinical Practice and with the Declaration of Helsinki (1989). The investigator will conduct all aspects of this study in accordance with all national, state, and local laws of the applicable regulatory agencies.

Most patients will be children, adolescents, and young adults because of the nature of these tumors. Patients of both sexes and all ethnic backgrounds are eligible for this study. Alternative treatments are available and will be discussed with patient or legal guardian. Patients are responsible for the costs of physician visits and usual (routine) laboratory tests, all scans, usual (standard) bone marrow tests, hospitalizations, and outpatient care, GM-CSF, and isotretinoin. There is no charge for 3F8. If there is an injury as a result of this research study, emergency care, hospitalization, and outpatient care will be made available by Memorial Hospital and billed to the patient as part of the medical expenses. No money will be provided by Memorial Hospital as compensation for research-related injury.

#### 17.1 Privacy

MSKCC's Privacy Office may allow the use and disclosure of protected health information pursuant to a completed and signed Research Authorization form. The use and disclosure of protected health information will be limited to the individuals described in the Research Authorization form. A Research Authorization form must be completed by the Principal Investigator and approved by the IRB and Privacy Board.

#### 17.2 Serious Adverse Event (SAE) Reporting

Any SAE must be reported to the IRB/PB as soon as possible but no later than 5 calendar days. The IRB/PB requires a Clinical Research Database (CRDB) SAE report be submitted electronically to the SAE Office at [[contact]](mailto:[contact]) containing the following information:

Amended: 02/24/15

## Memorial Sloan-Kettering Cancer Center IRB Protocol

IRB#: 09-159A(10)

### Fields populated from the CRDB:

- Subject's name (generate the report with only initials if it will be sent outside of MSKCC)
- Medical record number
- Disease/histology (if applicable)
- Protocol number and title

### Data needing to be entered:

- The date the adverse event occurred
- The adverse event
- Relationship of the adverse event to the treatment (drug, device, or intervention)
- If the AE was expected
- The severity of the AE
- The intervention
- Detailed text that includes the following information:
  - A explanation of how the AE was handled
  - A description of the subject's condition
  - Indication if the subject remains on the study
  - If an amendment will need to be made to the protocol and/or consent form

The PI's signature and the date it was signed are required on the completed report.

### For IND/IDE protocols:

The CRDB AE report should be completed as above and the FDA assigned IND/IDE number written at the top of the report. The report will be forwarded to the FDA by the Institutional SAE Manager through the IND Office.

### **17.2.1 All SAEs must be entered into the CRDB SAE form page.**

SAEs are defined as grade 4 toxicities other than fatigue, weight loss or weight gain, anorexia, nausea, anxiety, constipation, urinary retention from opioid analgesics, somnolence/hallucinations/ disorientation/confusion/ agitation/anxiety from anti-histamine and opioid premedications, hypomagnesemia, fever, rash, dry skin from Accutane, urticaria from 3F8 or GMCSF, myelosuppression from the combination of 3F8 and GM-CSF, pain and transient hypoxia from opioids, and breath-holding with or without transient oxygen requirement. Preexisting conditions e.g. hearing loss, hyperbilirubinemia or elevated LFTs from TPN, alopecia are not counted as SAEs. Hospitalizations that arise from complications of chemotherapy are considered part of standard care and therefore will not be reported.

Amended: 02/24/15

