**Note: If for any reason tests cannot be completed on day 0, they will be completed on day 1**

**\* Pretreatment evaluation should be completed within 30 days of treatment**

## 11.0 TOXICITIES/SIDE EFFECTS

**11.1** Toxicities are graded by the Common Toxicity Criteria (Version 3.0) developed by the National Cancer Institute (NCI) of the USA. All toxicities during cycle 1 will be recorded. After cycle 1, only toxicities  $\geq$  grade 3 will be recorded.

**11.2** 3F8: Reversible side-effects include pain, paresthesia, hypertension, hypotension, tachycardia, urticaria, fever, nausea, emesis, and rarely, diarrhea, serum sickness, hyponatremia, somnolence and posterior reversible encephalopathy syndrome (PRES). Other potential side-effects that may occur are bronchospasm, anaphylaxis, peripheral neuropathy, impaired accommodation of the eye and poor reactivity of pupils to light.

**11.2.1** The definition of unacceptable pain is the same as in the IRB 05-015 phase I 3F8 dose-escalation study, as reported71a:  $\geq 7$  doses of opioids administered within two hours. One dose of analgesic is defined as hydromorphone 0.015 mg/kg or equianalgesic dose of morphine sulfate.

**11.2.2** The definition of unacceptable hypertension is the same as in the IRB 05-015 phase I 3F8 dose-escalation study, as reported71a: hypertension necessitating medicinal intervention for  $>24$  hours.

Amended: 02/24/15

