### 14.0 BIOSTATISTICS

The objective of this phase II trial is to assess the anti-NB activity of high-dose 3F8 plus GM-CSF in patients in first CR/VGPR from high-risk NB after conventional therapy. The 3F8 dosing is four fold greater than the standard 3F8 dosage used in prior phase II studies.

In A(8), treatment was changed to use standard dose 3F8 ( $20 \text{ mg/m}^2/\text{day}$ ) for all cycles instead of high-dose 3F8 for cycles 1 and 2. Patients treated as such are evaluable for toxicity only.

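### The only SAE definition is a list-limited set of grade 4 toxicities, so fatal toxicities and serious toxicities below grade 4 do not, as written, trigger expedited reporting

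*Combined protocol and SAP*

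**What the plan says.** Section 17.2.1 sets the definition by severity grade: "SAEs are defined as grade 4 toxicities other than fatigue", followed by a long list of other exempt events. Death, grade 5 and lasting disability are not mentioned. Hospitalisation appears once, as an exclusion: "Hospitalizations that arise from complications of chemotherapy are considered part of standard care and therefore will not be reported".

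Three reporting steps depend on an event being an SAE:

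- Section 17.2: "Any SAE must be reported to the IRB/PB as soon as possible but no later than 5 calendar days".
- Section 17.2.1: entry on the CRDB SAE form page.
- Section 17.2, IND/IDE paragraph: "The report will be forwarded to the FDA by the Institutional SAE Manager through the IND Office". Section 5.1 gives an IND number for 3F8, so this paragraph applies.

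Toxicity is also captured outside SAE reporting. Section 11.1 says "All toxicities during cycle 1 will be recorded", and limits recording to grade 3 or higher after that. Section 16.2 plans a safety analysis of every patient given at least one dose, with adverse events tabulated by severity and by dosage, both single and cumulative.

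One of the two secondary objectives (section 2.0) is a safety objective for the high-dose treatment: "to assure no side-effects or noxious sequelae develop or emerge that were not seen in the prior phase I study". For patients treated at the standard dose from amendment A(8), section 14.0 says "Patients treated as such are evaluable for toxicity only".

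**The concern.** A severity grade is not a test of seriousness. A rule that stops at grade 4 leaves out the worst outcome, and it takes no account of consequences such as admission or lasting harm. Most patients will be children, and the agent is given under an IND. The IRB and the FDA would rely on prompt notice of a fatal or disabling toxicity, and the written rule does not require it.

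The chemotherapy exclusion raises a second problem. Section 9.1 lets patients whose treatment is delayed by HAMA receive low-dose chemotherapy or anti-HAMA agents, then resume 3F8/GM-CSF. An admission caused by that chemotherapy occurs on study, yet the wording of 17.2.1 would cover it just as it covers a complication of treatment given before enrolment.

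**Working it through.** No arithmetic applies to the definition. The check is to read 17.2.1 literally, follow each type of event through the channels the protocol describes, and look for any other text that would catch it.

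**Step 1: is there a second definition?** Section 13.3 mentions a Serious Event Report for patients removed because of adverse events, to be used where applicable, but does not define serious. Section 16.2 refers to institutional monitoring procedures in an appendix, but section 20.0 lists only patient diaries. Section 17.2.1 is therefore the only definition in the document.

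**Step 2: where does each type of event go?**

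| Event | SAE under 17.2.1, so 5-day IRB/PB report, SAE form and FDA forwarding | Recorded under 11.1 |
|---|---|---|
| Grade 4 toxicity not on the exception list | Yes | Yes |
| Grade 4 toxicity on the exception list | No | Yes |
| Fatal (grade 5) toxicity | No, as written | Yes |
| Grade 3 toxicity that hospitalises or disables | No | Yes |
| Grade 1-2 toxicity that hospitalises, cycle 1 | No | Yes |
| Grade 1-2 toxicity that hospitalises, after cycle 1 | No | No |

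Events in the last row miss both channels. The other non-SAE rows still reach the section 16.2 tabulation, but with no reporting deadline.

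**Step 3: do the protocol's own safety concerns fit the threshold?** Section 11.2 names posterior reversible encephalopathy syndrome as a rare side-effect of 3F8; at grade 3 it would not be an SAE even if the patient were admitted. Section 11.2.2 classes hypertension as unacceptable when it needs drug treatment for more than 24 hours. That criterion is a duration, so such an event is an SAE only if it is also graded 4.

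**Step 4: chemotherapy.** Set side by side, 9.1 permits chemotherapy during the study and 17.2.1 exempts hospitalisations from its complications without saying which chemotherapy is meant. Nor does the text say whether a grade 4 toxicity behind such an admission remains an SAE.

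**The case against.** The strongest reply is that the safety analysis does not run on SAEs. That stands. Sections 11.1 and 16.2 capture grade 3 and higher toxicities in every cycle and tabulate adverse events by grade and by 3F8 dose. A reader might infer that the safety objective would be assessed on filtered data, or that a new tabulation by dose is needed. The document does not support either inference.

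A second reply is that deaths would be reported in practice. Section 16.2 adopts the institution's phase II procedures, which include adverse event notification, and section 17.0 commits the trial to good clinical practice and applicable law. Excluding only chemotherapy-related admissions also suggests the authors assumed other admissions would count. This reply stands in part: one cannot conclude from the document that deaths would go unreported, and incomplete drafting is more likely than intent. But no rule covering them appears in the text that staff are told to follow.

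Three other stronger readings also fail:

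- Detecting new toxicity is not the trial's main aim. The primary objective is relapse-free survival, and the safety objective is worded for a high dose that new patients have not received since A(8).
- The list does not exempt all opioid-related hypoxia, only transient hypoxia. Whether 3F8 pain is exempt is unclear, because the opioid qualifier may or may not attach to pain.
- Saying that no grade 5 events reach the 5-day pathway restates the definition. It is not an estimate of events missed.

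Finally, a fix can overshoot. The design rates in section 14.2 are two-year relapse-free survival of 0.64 and 0.80, so 1 − 0.80 = 20% to 1 − 0.64 = 36% of patients fail by two years. Of 58 patients that is 0.20 × 58 = 11.6 to 0.36 × 58 = 20.9, or about 12 to 21. Without a limit to toxicities, admissions and deaths from relapse among them would become SAEs.

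**Conclusion.** The point holds as a gap in expedited reporting. Followed as written, 17.2.1 keeps a fatal toxicity, or a disabling or hospitalising toxicity below grade 4, out of the 5-day report, the SAE form and FDA forwarding. For serious toxicities below grade 3 after cycle 1, the gap extends to recording under 11.1. Separately, the chemotherapy-hospitalisation exclusion needs to be reconciled with 9.1.

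The gap cannot be sized, because the document gives no rates of fatal or serious toxicity. The conclusion rests on two assumptions: that staff apply the written definition literally, and that no institutional rule outside the document overrides it. If such a rule exists, the remedy is to state it in 17.2.1. The change is worth making because it is cheap and bears directly on patient safety. It does not call the planned efficacy or safety analyses into question.

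**What to change.** Reword 17.2.1 so that:

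1. SAEs are grade 4 or grade 5 toxicities, plus toxicities of any grade that cause or prolong hospitalisation or cause lasting disability.
2. The definition applies within a stated reporting window and excludes events due solely to disease progression.
3. The list of expected events remains exempt from expedited reporting, except when the outcome is death.
4. The chemotherapy-hospitalisation exclusion is reconciled with 9.1, saying explicitly how it treats chemotherapy given on study for HAMA.

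A cross-reference in 11.1, stating that SAEs are recorded at any grade in any cycle, would keep the two sections consistent.

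The cost is one paragraph in an amendment and some additional SAE reports. Limiting the definition to toxicities, with a window and the progression exclusion, keeps that number down. Treatment, eligibility and the efficacy analysis are unchanged.
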